5.1.2. Method of Assessing Treatment Compliance

The following measures will be employed to ensure treatment compliance. The single dose of IP should be administered under the supervision of clinical study personnel. For patients receiving the tablet formulation, a mouth and hand check of all patients should be carried out to ensure that all tablets have been swallowed, if applicable. For patients receiving the liquid oral suspension the clinic personnel will check and record whether any of the liquid is spit out or lost to drooling.

5.1.3. Labeling and Packaging

Investigational products will be packaged and labeled in an open-label format. Clinical study labels will include study number, contents, quantity, lot number, directions, storage conditions, CAUTION statement as required by country/region, and Sponsor information. In addition, oral syringes for dosing of reconstituted suspension will be provided by the Sponsor.

Edoxaban 30 mg tablets, expressed as the anhydrous free base, will be supplied by the Sponsor in blister cards containing 30 tablets, in an open-label format. The 60 mg edoxaban granules for reconstitution, will be packaged in amber glass bottles (wide neck) with white polypropylene caps, and supplied by the Sponsor.

5.1.4. Preparation

The IP will be provided as tablets and as a granule for oral suspension formulation.

No special preparation will be required for the tablet formulation.

For edoxaban (DU-176b) granule for oral suspension 60 mg, investigational product will be supplied in amber glass bottles (wide neck) with white polypropylene caps. The medication requires reconstitution with water and must be freshly prepared just prior to administration (within 30 minutes). The total amount of diluent (non-carbonated water) to be added is 8 mL, and added in 1 part. After reconstitution, the resultant drug concentration will be 6 mg/mL. The maximum amount of medication will be 10 mL. Aliquots appropriate to provide the required dose will be withdrawn from this 10 mL suspension. Before aliquoting, the bottle must be shaken. The edoxaban suspension is a single-use preparation for immediate use and is not intended to be stored.

5.1.5. Storage

Investigational products (edoxaban tablets and granules for reconstitution) must be stored at 20° to 25°C (68° to 77°F), with excursions permitted to 15° to 30°C (59° to 86°F). Drug supplies must be stored in a secure, limited access storage area under the recommended storage conditions. If storage conditions go outside of the specified range, DSI should be contacted. The excursions will be discussed with the Sponsor to determine what action is necessary.

5.1.6. Drug Accountability

When a drug shipment is received, the Investigator or designee will check the amount and condition and temperature recording of the drug, check for appropriate local language in the label, drug expiration date, and sign the Receipt of Shipment Form provided. The Receipt of Shipment Form should be faxed as instructed on the form. The original will be retained at the site. In addition, the Investigator or designee shall contact the Sponsor as soon as possible if there is a problem with the shipment and quarantine the shipment until resolution is obtained from the Sponsor.

A Drug Accountability Record will be used for the IP, and can be provided by the Sponsor/Sponsor representative, or the site can use a Sponsor Approved Form. The record must be kept current and should contain the dates and quantities of drug received, patients for whom the IP was dispensed (identification number and/or initials or supply number as applicable), the date and quantity of IP dispensed and remaining, if from individual patient drug units, as well as the initials of the dispenser.

At the end of the study, or as directed, all IP, including unused, partially used, or empty containers, will be destroyed at the clinic. The IP will only be returned to a designee as instructed by the Sponsor if the clinic is unable to perform the IP destruction. Dosage form (ie, tablet, granule bottle) site level accountability documentation is required as part of the disposition records of the investigational product. The dosage form site level accountability documentation should be appended to the Certificate of Destruction.

Investigational product will be returned only after the study monitor has completed a final inventory to verify the quantity to be returned. The return/destruction of IP must be documented. Dosage form (ie, tablet, granule bottle) site level accountability documentation must be included with each drug supply return shipment or other returning facility, such as another depot. This is required as part of the receiving records for return shipments.

At the end of the study, a final IP reconciliation statement must be completed by the Investigator or designee and provided to the Sponsor. Unused drug supplies may be destroyed by the Investigator when approved in writing by the Sponsor and the Sponsor has received copies of the site's drug handling and disposition standard operating procedures (SOPs).

All IP inventory forms must be made available for inspection by a Sponsor-authorized representative or designee and regulatory agency inspectors. The Investigator is responsible for the accountability of all used and unused study supplies at the site.

5.1.7. Retention Samples

Retention samples will be collected and stored in countries where required by regulations.

5.2. Concomitant Medications

For the below specified number of days through study completion or upon early withdrawal, the following medications are not allowed:

- Use of P-gp inhibitors or inducers (see Appendix 17.4) within 14 days prior to the edoxaban dose until after the last PK sample is collected.
- Use of any CYP3A4 inhibitors/inducers (see Appendix 17.3) for 14 days prior to edoxaban dose to until after the last PK sample is collected.

- Use of nonsteroidal anti-inflammatory drugs (such as ibuprofen), and antiplatelet (except low-dose aspirin [1 to 5 mg/kg/day, maximum of 100 mg/day]) from 14 days prior to edoxaban dose to until after the last PK sample is collected. Patients on low-dose aspirin treatment (1 to 5 mg/kg/day, maximum of 100 mg/day) are permitted to participate in the study per the Investigator's judgment that this does not place the patients at an unacceptable bleeding risk. Low-dose aspirin on Day 1 should be withheld until 4 hours post edoxaban dose.

During the study, concomitant medications required for care of treatment-emergent AEs (TEAEs) will be permitted; although, where possible, the Investigator should speak with the DSI Medical Monitor and Study Director before prescribing such medication. For treatment of pain or for analgesic use, if needed, acetaminophen is recommended.

Any medication (other than study drug) taken by patients during the course of the study will be recorded and coded using the World Health Organization drug dictionary. If drug therapy other than that specified by the protocol is taken, a joint decision will be made by the Investigator and Sponsor to continue or discontinue the patient.

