Edoxaban is primarily eliminated unchanged in urine and through biliary secretion; with metabolism contributing to a lesser extent towards total clearance of edoxaban. In healthy volunteers, edoxaban is the predominant excreted component in urine, accounting for 24% of the administered dose. In feces, it accounts for 49% of administered dose (Study PRT019). In healthy volunteers, renal and nonrenal clearances contribute equally (approximately 50% each) to the total clearance of edoxaban. The human-specific metabolite, D21-2393, is not detected in urine and only about 2% is detected in feces (A-U139 and PRT019).

In drug interaction studies with P-gp inhibitors (erythromycin, ketoconazole, cyclosporine, and verapamil), exposure of edoxaban increased, but the increase was generally less than 2-fold.

Other drug interaction studies with inhibitors of P-gp and/or other CYPs (quinidine, amiodarone, and dronedarone) also resulted in less than 2-fold increase in edoxaban exposure.

When edoxaban is dosed with a high-fat meal, there is no change in total exposure, but peak exposure increases by about 40%.

Concomitant administration of anti-platelet drugs (aspirin [100 and 325 mg qd \times 5 days] and naproxen [500 mg bid \times 2 days]) was assessed by investigating PK and bleeding times.

Edoxaban exposure was either not affected or minimally affected by concomitant aspirin and naproxen. In all 3 studies, bleeding times increased after administration of edoxaban, but to a lesser extent than those observed with either of the anti-platelet agents alone. Administration of edoxaban in combination with the anti-platelet agents resulted in longer bleeding times than observed for any of the drugs alone. The inter-study comparisons of edoxaban coadministered with either 100 or 325 mg aspirin indicated no significant difference in bleeding times by aspirin dose in these short-term studies. Patients who received edoxaban and aspirin 325 mg had more bleeding adverse events (AEs) than those treated with edoxaban alone or aspirin alone. However, the data are limited and until there is further experience, the dose of aspirin coadministered with edoxaban should be limited to 100 mg in the absence of a compelling indication (e.g., acute myocardial infarction to reduce the risk of bleeding).

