2. Male or female patients 38 weeks gestation to < 18 years of age on the day of dosing.
3. Patients 2 to < 18 years of age must have a body mass index (BMI) between the 5th and 95th percentile based on the 2000 CDC Growth Charts⁷ (the maximum number of patients in each dose group that have a BMI between the 85th and 95th percentile should not be more than 2 patients). Patients < 2 years of age must have a body weight between the 5th and 90th percentile based on the 2000 CDC Growth Charts.⁷
4. Female patients who have had menarche must test negative for pregnancy, as per local practice, at screening and check-in.
5. Female patients who have had menarche and are sexually active must agree to use an effective contraception method, per local practice, for at least 30 days prior to edoxaban dose.
6. Patients/legal guardian(s) must agree to food and drug restrictions during the study.
 - Patients must agree to abstain from and/or legal guardians must agree not to give the patient cola, tea, coffee, chocolate, and other caffeinated drinks and food from 48 hours before dose administration to until after the last PK sample collection (see Section 5.3 for a complete list). Mothers who are breastfeeding study patients should maintain this same dietary restriction for 24 hours prior to edoxaban dosing.
 - Patients must agree to abstain from and/or legal guardian(s) must agree not to give the patient St. John's Wort and food/supplement and beverages containing grapefruit, grapefruit juice, and Seville oranges from 14 days before the first dose through to until after the last PK sample collection (see Section 5.3).

- Patients must agree to abstain from CYP3A4 inhibitors/inducers and P-gp inhibitors/inducers for 14 days prior to the edoxaban dose to until after the last PK sample collection (see Section 5.2).
7. Patients must agree to abstain from the use of nonsteroidal anti-inflammatory drugs (such as ibuprofen) and antiplatelet (except for low-dose aspirin) from 14 days prior to edoxaban dose until after the last PK sample is collected. Patients on low-dose aspirin treatment (1 to 5 mg/kg/day, maximum of 100 mg/day) are permitted to participate in the study per the Investigator's judgment that this does not place the patients at risk. Low-dose aspirin on Day 1 should be withheld until 4 hours post edoxaban dose.

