Exact dates and times of dosing and sample collection will be recorded in the patients' CRFs and used for analyses. At time points when PK, and PD blood samplings occur at the same time, the PK blood samples will be collected first and then PD blood samples will be collected. An overnight stay on Day 1 is not mandatory.

6.3.3.2. Day 2

On Day 2, the following procedures will be performed:

- **All Cohorts:**

- AE monitoring.
- Concomitant medication monitoring.

- **Cohort 1, 2, and 3:**

- PK blood samples will be collected using a window approach at 24 to 36 hours postdose.
- PD blood samples for estimation of biomarkers of coagulation (aPTT, PT, and anti-FXa) immediately after collection of the simultaneously scheduled PK samples at 24 to 36 hours postdose.

- **Cohort 4:**

- PK blood samples will be collected using a window approach at 24 to 36 hours postdose.

- **Cohort 5:**

- Note: For this cohort, only 3 of 4 possible PK timepoints will provide a blood specimen. For patients who provided only 2 PK blood samples on Day 1, a 3rd PK

blood sample will be collected at 24 to 36 hours. No PK blood samples will be collected for patients who provided 3 PK blood samples on Day 1.

Note: the overnight stay on Day 1 is not required; however, the above procedures will occur on Day 2. Some patients may be given the option to have a home healthcare service conduct the Day 2 procedures in the patient's home, depending on the availability of the service in the patient's country. Exact dates and times of dosing and sample collection will be recorded in the patients' CRFs and used for analyses. At time points when PK and PD blood samplings occur at the same time, the PK blood samples will be collected first and then PD blood samples will be collected.

6.3.3.3. Day 3

On Day 3, the following procedures will be performed:

- **PK blood samples for Cohort 1:** will be collected using a window approach at 48 to 54 hours postdose.
- Vital signs (including blood pressure, pulse rate, and body temperature) will be taken 48 to 54 hours postdose. All vital sign assessments will be performed before the scheduled blood sampling for edoxaban and after at least a 5-minute rest in a sitting or supine position. The position in which the vital signs are taken (i.e., sitting or supine) will be recorded in the CRF.
- AE monitoring.
- Concomitant medication monitoring.

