4. Sampling scheme may be adjusted for various age cohorts based on emerging PK and safety data. The patient will check-out after the last PK sample has been collected on Day 2. Note: Blood is collected at only 3 of the 4 timepoints for Cohort 5; the timepoint 0.5 to 2 hours is mandatory.
5. To be concurrent with PK sampling, after PK sampling based on age cohort.

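### The NSAID and antiplatelet ban ends at the last PK sample, so under one of three permitted Cohort 5 schedules it lapses 9 to 14 hours after edoxaban (minor gap, cheap to close)

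*Combined protocol and SAP*

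**What the plan says.** Section 5.2 prohibits NSAIDs and antiplatelets, apart from low-dose aspirin, "from 14 days prior to edoxaban dose to until after the last PK sample is collected". Inclusion criterion 7 (Section 4.1.1) sets the same limits: "from 14 days prior to edoxaban dose until after the last PK sample is collected". The P-gp and CYP3A4 restrictions in Section 5.2 end at the same sample.

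Low-dose aspirin (at most 100 mg/day) is handled separately. It is allowed if the Investigator judges that "this does not place the patients at an unacceptable bleeding risk", and it has its own timing rule: "Low-dose aspirin on Day 1 should be withheld until 4 hours post edoxaban dose". Section 5.2 also permits medication needed to treat treatment-emergent adverse events (TEAEs), and it recommends acetaminophen for pain.

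For Cohort 5, note 4 to Table 17.4 (Section 17.7) says "Blood is collected at only 3 of the 4 timepoints for Cohort 5; the timepoint 0.5 to 2 hours is mandatory". The Day 2 instructions (Section 6.3.3.2) add "No PK blood samples will be collected for patients who provided 3 PK blood samples on Day 1". The Sponsor assigns the timepoints (Sections 6.3.3.1 and 8.1.1).

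On the interaction itself, Section 1.1.1.5 reports from adult studies that "Edoxaban exposure was either not affected or minimally affected by concomitant aspirin and naproxen", and that "Administration of edoxaban in combination with the anti-platelet agents resulted in longer bleeding times than observed for any of the drugs alone".

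**The concern.** A restriction that protects PK data can reasonably stop when the last PK sample is drawn. A restriction that guards against bleeding should depend on how long ago the anticoagulant was given. The adult data in Section 1.1.1.5 point to the second purpose for NSAIDs and antiplatelets, since they barely change edoxaban exposure but lengthen bleeding time in combination with it.

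In Cohorts 1 to 4 the distinction has no practical effect, because the last sample falls at 24 hours or later. In Cohort 5, two infants given the same drug can leave the ban many hours apart solely because of the sampling windows they were assigned. Cohort 5 is also the youngest group, and Section 1.1.1.4 notes that the kidneys are immature at birth. After the early lapse, Section 5.2 places no dose cap and requires no bleeding-risk judgment for NSAIDs or for antiplatelets other than low-dose aspirin.

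**Working it through.** The plan gives no figure of its own on this point. The check is a count of the permitted schedules, followed by simple differences.

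**Does the Section 5.2 lead-in extend the ban?** It says the restrictions run through study completion. Section 4.2.1 counts a patient as complete once the last scheduled PK sample is given. The lead-in therefore adds no time.

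**Cohort 5 schedules** (windows from Sections 6.3.3.1 and 8.1.1). The 0.5 to 2 h sample is fixed, and two of the other three windows are chosen: C(3,2) = 3.

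| Schedule | Windows (h after dose) | Ban ends |
|---|---|---|
| (a) | 0.5–2, 3–8, 9–14 | 9–14 h |
| (b) | 0.5–2, 3–8, 24–36 | 24–36 h |
| (c) | 0.5–2, 9–14, 24–36 | 24–36 h |

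Schedule (a) is not a contrived case, because Section 6.3.3.2 provides for infants who give three samples on Day 1.

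**Other cohorts** (Section 8.1.1). Cohorts 2, 3 and 4 have a last sample at 24 to 36 h, and Cohort 1 at 48 to 54 h.

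**Size of the difference.**
- Earlier end under (a) than under (b) or (c): smallest 24 − 14 = 10 h, largest 36 − 9 = 27 h. The upper figure pairs the extremes of two windows.
- Shortfall of (a) against 24 h: 24 − 14 = 10 h to 24 − 9 = 15 h.

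**Number affected.** Cohort 5 is 12 of 60 evaluable patients (12/60 = 20%). The documents do not give the split across schedules, so the number on (a) is 0 to 12. If the three were used equally, which is an assumption, it would be 12/3 = 4.

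**How much drug might remain (adult context only).** Section 1.1.1.5 gives an oral terminal half-life of 10 to 14 h. It also gives a steady-state peak of 303 ng/mL and a trough of 15.5 ng/mL at 60 mg.
- Half-lives elapsed at 9 to 14 h: 9/14 = 0.64 to 14/10 = 1.4. At 24 h: 24/14 = 1.7 to 24/10 = 2.4.
- Taking the trough as the 24 h level and extrapolating back by 15.5 × 2^((24 − t)/half-life): the lowest value is 25.4 ng/mL (t = 14 h, half-life 14 h) and the highest 43.8 ng/mL (t = 9 h, half-life 10 h).
- Against the peak: 25.4/303 = 8.4% to 43.8/303 = 14.5%.

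By these adult figures, some drug is still present when the ban lapses, at a small fraction of the peak. The documents give no corresponding infant figure.

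**The case against.** The strongest case against is that this is a permissible design choice.

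- **Purpose.** No section says why the ban exists. A reader might infer from the bleeding-risk phrase in Section 5.2 that bleeding is its documented reason, but that phrase belongs to the aspirin exception. The bleeding purpose is an inference from Section 1.1.1.5. This objection stands, and the point rests on likelihood only.
- **The 24 h figure.** The protocol's 24 h interval (Section 4.1.1) is for restarting low molecular weight heparin (LMWH), a different drug class. The nearer comparator is low-dose aspirin, which is allowed from 4 h, so the protocol does not demand 24 antiplatelet-free hours. This also stands. The aspirin allowance is, however, capped and subject to Investigator judgment, whereas nothing comparable applies to other agents after the lapse.
- **Narrow exposure.** Enrolled infants have been off these drugs for 14 days. An NSAID or antiplatelet would have to be started or resumed within a 10 to 15 h period for a reason other than a TEAE. Acetaminophen is the recommended analgesic, patients with high bleeding risk are excluded (Section 4.1.2), and adverse events and concomitant medication are monitored on Day 2 and at follow-up. All of this stands and keeps the point minor.
- **No shown harm.** Section 1.1.1.5 describes repeated adult dosing of aspirin and naproxen. It does not test an NSAID first taken 9 to 14 h after edoxaban. A reader might infer an excess bleeding risk in these infants, but the documents do not support any rate.

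The objections do not answer the central observation: the length of this ban is set by which PK windows the Sponsor assigns, and nothing in the protocol suggests that was intended.

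**Conclusion.** The gap is real and minor. Under one of three permitted Cohort 5 schedules the ban on NSAIDs and antiplatelets other than low-dose aspirin lapses 9 to 14 h after edoxaban. Under the other two, and in every other cohort, it lasts at least to the 24 to 36 h sample. The schedule count and the end times follow directly from the text. Calling it a safety gap depends on one assumption, that the ban is at least partly a bleeding precaution. The adult data make this likely, but the protocol does not say it.

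One in three counts schedules, not patients. A reader might take it as a third of Cohort 5, but the documents give no allocation, so the number affected could be anywhere from 0 to 12. No bleeding rate can be derived, and expected harm is small.

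**What to change.** In Section 5.2 and inclusion criterion 7, end the ban on NSAIDs and antiplatelets other than low-dose aspirin at the later of the last PK sample and 24 hours after the edoxaban dose. Keep the low-dose aspirin allowance from 4 hours and the allowance for treating TEAEs. Leave the P-gp, CYP3A4 and dietary restrictions tied to the last PK sample. The 24 h floor is pragmatic, by analogy with the LMWH restart interval, and is not an existing rule for NSAIDs.

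The cost is one clause in two places, 10 to 15 more hours of restriction for infants on schedule (a), and an amendment with IRB/IEC approval (Section 15.1). No extra draw, visit or stay is needed. Schedules (b) and (c) and Cohorts 1 to 4 are unchanged, because their last sample is already at 24 h or later. The documents mention no forthcoming amendment that could carry the change, and it helps only if it is in place before the schedule (a) infants are dosed.

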5.3. Lifestyle Guidelines

At screening, patients/legal guardians will be informed that if accepted for the study, no St. John's Wort or foods/supplements or beverages containing grapefruit, grapefruit juice, or Seville oranges are allowed for 14 days prior to dosing to until after the last PK specimen collection. Patients must agree to abstain from and/or legal guardians must agree not to give the patient cola, tea, coffee, chocolate, and other caffeinated drinks and food from 48 hours before dose administration through the end of the last PK specimen collection. Mothers who are breastfeeding study patients should maintain this same dietary restriction for 24 hours prior to edoxaban dosing.

6. STUDY PROCEDURES

A study visit schedule in tabular format is provided in Appendix [17.7](#). To minimize pain and distress for pediatric patients, the following measures are allowed:

- Use of topical anesthetics
- Use of indwelling cannula

However, heparin should not be used for flushing the cannula.

